## **8. INFORMED CONSENT, DATA PROTECTION, STUDY RECORDS**

The PMS will be carried out in routine clinical practice without any intervention involving the patients, and there is no restriction on daily clinical practice. Principles are specified in accordance with the Japanese GPSP regulations (Ministry of Health and Welfare Ordinance No.1711, December 12, 2004), Japanese Good Vigilance Practice (GVP) regulations (Ministry of Health and Welfare Ordinance No.1315, October 22, 2004) and relevant BI Standard Operating Procedures (SOPs). Standard medical care (prophylactic, diagnostic and therapeutic procedures) remains the responsibility of the patient's treating physician.

The rights of the investigator and of the sponsor with regard to publication of the results of this PMS are described in the contract. As a general rule, no PMS results should be published prior to finalisation of the Study Report.

### **8.1 STUDY APPROVAL, PATIENT INFORMATION, AND INFORMED CONSENT**

The review by IRB is not mandatory for conducting PMS in Japanese GPSP, due to the fact that required PMS by MHLW is an observational study using market products involved in normal therapeutic procedures without any interventional procedure.

The same applies for the implementation of changes introduced by amendments. The sponsor will enter into a contract with a representative, e.g. head of hospital, in accordance with GPSP.

Written informed consent prior to patient participation in the trial is not regulatory or legal requirements in accordance with GPSP.

### **8.2 DATA QUALITY ASSURANCE**

This PMS is to be conducted in accordance with both the in-house PMS SOP and working instructions which are in compliance with GPSP.

### **8.3 RECORDS**

Case Report Forms (CRFs) for individual patients will be provided by the sponsor via an Electronic Data Capture (EDC) system.

#### **8.3.1 Source documents**

Source documents provide evidence for the existence of the patient and substantiate the integrity of the data collected. Source documents are filed at the investigator's site.

Data entered in the eCRFs that are transcribed from source documents must be consistent with the source documents or the discrepancies must be explained. The investigator may need

to request previous medical records or transfer records, depending on the trial; also current medical records must be available.

For eCRFs, all of the following data must be derived from source documents.

- Patient identification (gender, date of birth)
- Patient participation in the PMS (substance, patient number)
- Dates of Patient's visits, including dispensing of medication
- Medical history (including indication and concomitant diseases, if applicable)
- Medication history
- Adverse events and outcome events (onset date, end date, treatment for AEs)
- Serious adverse events (onset date, and end date)
- Laboratory results

### **8.3.2 Direct access to source data and documents**

The investigator / institution will permit PMS-related regulatory inspection, providing direct access to all related source data / documents. All source documents, including progress notes and copies of laboratory and medical test results, must be available at all times for inspection by health authorities (e.g. PMDA). The accuracy of the data will be verified by reviewing the documents described in Section [8.3.1](#)

## **8.4 STATEMENT OF CONFIDENTIALITY**

Individual patient medical information obtained as a result of this PMS is considered confidential and disclosure to third parties is prohibited with the exceptions noted below. Patient confidentiality will be ensured by using patient identification code numbers.

Data generated as a result of the PMS needs to be available on request by the regulatory authorities.

## **8.5 COMPLETION OF STUDY**

Completion of the PMS will be notified to PMDA when the re-examination document is applied to in accordance with J-PAL and GPSP.

### **9.2 UNPUBLISHED REFERENCES**

## **10. APPENDICES**

Not applicable.

**11. SUMMARY OF NON-INTERVENTIONAL STUDY  
PROTOCOL MODIFICATIONS**

Summary of Modifications Sheet (SOMS)

Number of Protocol modification		
Date of Protocol modification		
BI Trial number		
BI Product(s)		
Title of protocol		
To be implemented only after approval of the IRB/IEC/Competent Authorities		
To be implemented immediately in order to eliminate hazard – IRB / IEC / Competent Authority to be notified of change with request for approval		
Can be implemented without IRB/IEC/ Competent Authority approval as changes involve logistical or administrative aspects only		
Section to be changed		
Description of change		
Rationale for change

2. LIST OF ABBREVIATIONS

Include a list of all abbreviations used in the TSAP

Term	Definition / description
ADR	Adverse drug reaction
AE	Adverse event
BICMQ	Boehringer Ingelheim customised MedDRA query
BMI	Body-mass index
CRF	Case Report Form
DBP	Diastolic blood pressure
ECG	Electrocardiogram
eGFR	Estimated Glomerular filtration Rate
FPG	Fasting plasma glucose
MedDRA	Medical Dictionary for Regulatory Activities
NGSP	National Glycohemoglobin Standardization Program
NIS	Non-interventional Study
PMS	Post Marketing Surveillance
PT	Preferred term
PV	Protocol violation
SBP	Systolic blood pressure
SD	Standard deviation
SMQ	Standardised MedDRA query
SOC	System organ class

3. INTRODUCTION

The purpose of this document is to provide a more technical and detailed elaboration of the principal features of the analysis described in the protocol, and to include detailed procedures for executing the statistical analysis of the post-marketing surveillance (PMS) data.

This Trial Statistical Analysis Plan (TSAP) assumes familiarity with the Non-interventional Study (NIS) Protocol, including Protocol Amendments. In particular, the TSAP is based on the planned analysis specification as written in NIS Protocol Section 7 “Statistical Methods and Determination of Sample Size”. Therefore, TSAP readers may consult the NIS Protocol for more background information on the study, e.g., on study objectives, study design and population, treatments, definition of measurements and variables, planning of sample size.

SAS[®] Version 9.4 or later version will be used for all analyses.

4. CHANGES IN THE PLANNED ANALYSIS OF THE STUDY

There has been no change in the planned analysis from the statistical methods described in the NIS Protocol.

5. ENDPOINT(S)

5.1 PRIMARY ENDPOINT(S)

There is no primary endpoint for efficacy, the primary objective of the PMS study is the evaluation of safety (see the NIS Protocol Section 5.2.1).

[figure not shown]
[figure not shown]
5.2 SECONDARY ENDPOINT(S)

[figure not shown]
5.2.1 Key secondary endpoint(s)

[figure not shown]
This section is not applicable as no key secondary endpoint has been specified in the NIS protocol.

[figure not shown]
5.2.2 Secondary endpoint(s)

[figure not shown]
The secondary endpoints will be used as stated in the NIS Protocol Section 5.1.1.

[figure not shown]

[figure not shown]

[figure not shown]

6. GENERAL ANALYSIS DEFINITIONS

6.1 TREATMENT(S)

For basic study information on treatments, please refer to NIS Protocol Section 4. The technical specification for treatment set-up is described in the analysis data set (ADS) plan. For efficacy analyses, data up to 7 days after last treatment intake will be considered as on treatment for HbA1c and 1 day for FPG. For safety analyses, data up to 7 days after last treatment intake will be considered as on treatment for AE, 1 day for weight, blood pressure and pulse and 3 days for laboratory measurements.

6.2 IMPORTANT PROTOCOL VIOLATIONS

The following table defines the different categories of important PVs. The right-most column describes which PVs will be used to exclude patients from the different patient analysis sets. The final decision about which patients will be excluded from analysis sets will be taken during the course of the study and at report planning meetings before database lock at the latest.

Table 6.2: 1 Important protocol violations

Category/ Code	Description	Example/Comment	Method	Excluded from
A	Entrance criteria not met			
A1.1	No type 2 diabetes		Automated	Efficacy
A1.2	Patient received JARDIANCE [®] treatment before registration		Manual	All
B	Informed consent			
C	Trial medication and randomisation			
C1	Incorrect trial medication taken			
C1.1	No treatment with JARDIANCE [®]		Automated	All
E	Missing data			
E1	No baseline value	No available baseline value of HbA1c and FPG for efficacy analysis	Automated	Efficacy
G	Trial specific			
G1	Invalid registration			
G1.1	No patient visit after entry	Patient made no visit after the entry	Automated	All
G1.2	Multiple registration	Patient who were already registered in this trial or over the two trials(1245.94 and 1245.98) with another patient ID In this case, all data for the later patient will not be used.	Manual	All
G1.3	Registration rule not followed		Manual	All
G1.4	Patient started JARDIANCE [®] treatment out of registration period	Patients who started treatment after the end of registration period(31May2017) *Patients who started before contract period are not entered.	Automated	All
G1.5	Not continuous investigation		Manual	All

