## FLOW CHART

	Screening	Treatment	End of Trial
Observation period*	Before first administration of JARDIANCE® Tablets	12, 26, 40, 52, 64, 78, 104, 130 W	156 W 
Registration	X 		
Demographics	X		
Administration of JARDIANCE® Tablets		X	X
Medical History/ Concomitant disease	X		
Waist circumference	X		
Blood pressure pulse rate and ECG	X	X	X
HbA1c and fasting plasma glucose	X	X	X
Laboratory tests	X	X	X
Physical examination (Body weight, height)	X	X 	X 
12-lead ECG	X	X	X
Pregnancy status 	X	X	X
Concomitant drug(s) and antidiabetic therapy 	X	X	X
Adverse events ██████████		X	X

W: Weeks

\*: Time points during the observation period are approximate. Collected data should be reported as of the closest available visit.

1: Patients administered JARDIANCE® Tablets will be registered preferably within 14 days from the day of first administration.

2: Body weight only

3: Only for female patients

4: From 1 month before first administration of JARDIANCE® Tablets

5: Time point for 156 weeks should be more than 1092 days.

Electronic case report form (eCRF): At 12 weeks, 52 weeks, 104 weeks, 156 weeks or discontinuation and each time when an adverse event has occurred, data in corresponding observation period should be entered into eCRF and transmitted using the EDC system.

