### 3. DESCRIPTION OF DESIGN AND STUDY POPULATION

#### 3.1 OVERALL DESIGN AND PLAN

This PMS is a prospective study using a continuous investigation system. Patients with type 2 diabetes mellitus will be included in the surveillance. No specific criteria (e.g., demographics, baseline characteristics, concomitant drugs in use) are defined for patient enrolment.

[figure not shown]
Patients administered JARDIANCE® Tablets will be registered preferably within 14 days from the day of first administration. Patients will be observed for up to 156 weeks (approximately 36 months) after start of the treatment with JARDIANCE® Tablets or at premature discontinuation and dropout. Observations are made at the following time points: before first administration of JARDIANCE® Tablets (screening, this visit is defined as baseline) and 12, 26, 40, 52, 64, 78, 104, 130 and 156 weeks after the start of treatment, or at discontinuation.

There are 4 separate eCRFs for 0-12 (Book 1), 13- 52 (Book 2), 53- 104 (Book 3) and 105-156 weeks (Book 4).

[figure not shown]
At 12, 52, 104 and 156 weeks after the start of treatment or at discontinuation, data are to be transmitted immediately after entered into eCRF. In case of occurrence of any adverse events, data in corresponding observation period should be immediately entered into eCRF and transmitted.

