**3.3 SELECTION OF POPULATION**

Total number of entered patients is 3,000 patients with the assessment of 3-year completed administration.

No limitations are set up on background factors of patients and their concomitant drugs in use of actual medical practice.

Estimated number of enrolled patients with renal dysfunction ( $45 \text{ mL/min/1.73m}^2 \leq \text{eGFR} < 60 \text{ mL/min/1.73m}^2$ ) is 100.

Grades for renal dysfunction are as follows.

Normal:  $\text{eGFR} \geq 90 \text{ mL/min/1.73m}^2$   
Mild:  $\text{eGFR} \geq 60 \text{ mL/min/1.73m}^2$  and  $< 90 \text{ mL/min/1.73m}^2$   
Moderate:  $\text{eGFR} \geq 30 \text{ mL/min/1.73m}^2$  and  $< 60 \text{ mL/min/1.73m}^2$   
Severe:  $\text{eGFR} < 30 \text{ mL/min/1.73m}^2$

Estimated number of enrolled elderly patients ( $\geq 75$  years) is 100.

Estimated number of enrolled patients with hepatic dysfunction is 100.

Patients with hepatic dysfunction: Investigator judgment is moderate or severe.

Investigator should judge the grade for hepatic dysfunction by using lab data category as described below and symptoms/concomitant diagnoses.

Normal: Normal AST/ALT  
Mild: AST/ALT >ULN and <3x ULN  
Moderate: AST/ALT ≥3xULN and <5x ULN + total Bil ≤ 2xULN  
Severe: AST/ALT ≥5 xULN, or AST/ALT ≥3xULN and <5x ULN + total Bil > 2xULN  
ULN is taken from the corporate standard reference range (001-MCG-157\_RD-01: Standard Ranges).

Sites throughout entire country will be equally listed according the size of the hospitals or general clinics at which JARDIANCE® Tablets are available for prescription.

Expected number of patients per site is 5-30 patients. Patients will be selected by using the continuous investigation system. The continuous investigation system is commonly used in Japanese PMS and accepted as a patient selection process by the PMDA.

Continuous investigation system is a method of registration that the investigator enrolls the patients who will start administration of marketed product into the PMS continuously (without exception) until the requested number of patients is reached.

Preferably, investigators will register patients within 14 days including the day on which the administration of JARDIANCE® Tablets is started. However, patients who are registered over 15 days after starting administration of JARDIANCE® Tablets are also used for safety and efficacy analysis.

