### **3.3.2 Inclusion criteria**

Patients with type 2 diabetes mellitus who have never been treated with JARDIANCE® Tablets / Empagliflozin before enrollment will be included.

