## **5.4 OTHER**

### **5.4.1 Other parameter**

#### **Demographics and history**

Demographics (gender, date of birth, indication, pregnancy status, height, body weight, waist circumference, hypersensitivity factor, alcohol habit, pre-treatment drug, diagnosed date of type 2 diabetes mellitus, smoking history, start date of administration)

Medical history (malignant tumor, cardiovascular/cerebrovascular disease (severity for cardiac failure for patients with past history of cardiac failure (NYHA classification)), urinary tract infection, genital infection, hypertension, osteoporosis, dyslipidaemia, goat/hyperuricaemia, others)

Concomitant disease (malignant tumor, cardiovascular/cerebrovascular disease (severity for cardiac failure for patients with past history of cardiac failure (NYHA classification)), urinary tract infection, genital infection, osteoporosis, others), presence or absence of diabetic concomitant diagnosis (neuropathy/nephropathy/retinopathy), degree of renal/hepatic functions at baseline, history of antidiabetic treatment (drug therapy, diet therapy)

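### SAP violation code A1.2, read literally, removes from both analysis sets every patient registered after the first dose, whom protocol 3.3 keeps

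*SAP*

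**What the plan says.** **SAP.** Table 6.2: 1 (SAP 6.2) has a category for unmet entrance criteria with two rows. A1.1 is absence of type 2 diabetes. A1.2 is "Patient received JARDIANCE [®] treatment before registration". A1.2 is assessed manually, has no entry in the comment column, and is marked *All* in the exclusion column. SAP 6.3 defines the safety set as patients with no violation marked *All* and draws the efficacy set from it. One A1.2 flag therefore takes a patient out of both.

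**Protocol on registration.** Section 3.1 and Flow Chart footnote 1 say that treated patients "will be registered preferably within 14 days from the day of first administration". Section 3.3 repeats this: "Preferably, investigators will register patients within 14 days including the day on which the administration of" the drug begins. It then adds that "patients who are registered over 15 days after starting administration of" JARDIANCE "are also used for safety and efficacy analysis".

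**Protocol on prior use.** Section 3.3.2 admits patients never treated with JARDIANCE or "Empagliflozin before enrollment will be included". The synopsis has a similar criterion, also tied to enrolment.

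**The concern.** Registration and first dose are separate dated events in this study, and the protocol lets the first come after the second. A rule that excludes anyone dosed before registration then catches patients who were registered as the protocol allows. It also catches the late registrants whom 3.3 explicitly keeps.

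What is at stake is membership of the safety set, and so both the numerator and the denominator of the primary endpoint. Table 6.2: 1 is the rule that staff apply patient by patient. If it is followed as written, the analysed population differs from the one in protocol 3.3, although SAP 4 declares no change from the protocol's planned analysis.

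**Working it through.** No arithmetic settles this point; it is a comparison of rules.

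**Step 1: apply each rule to each kind of patient.**

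| Patient | A1.2 as worded (SAP 6.2, 6.3) | Protocol 3.1, 3.3, 3.3.2 |
|---|---|---|
| Registered before first dose, no earlier use | Kept | Kept |
| Registered on the day of first dose | Depends on which came first that day | Kept |
| Registered after first dose, within the preferred 14 days | Excluded from both sets | Kept |
| Registered beyond the preferred period | Excluded from both sets | Kept in both analyses by explicit statement |
| Had an earlier course of the drug | Excluded from both sets | Does not meet 3.3.2 |

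The rules agree on the first and last rows. They conflict on the third and fourth, and A1.2 gives no clear answer on the second.

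**Step 2: find what A1.2 was probably meant to do.** Protocol 3.3.3 lists no exclusion criteria, so the entry conditions are type 2 diabetes and no previous use. A1.1 covers the first, which leaves A1.2 for the second. The assessment method points the same way. Registration date (protocol 3.3) and start date of administration (protocol 6.1) are both entered in the eCRF, so the literal rule would be a simple date comparison. G1.4, which does check a start date against a cut-off, is marked *Automated*; A1.2 is marked *Manual*. A manual check fits a search of the treatment history for an earlier course.

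**Step 3: see whether the protocol settles the wording.** It does not. Section 3.3 describes its method of registration in terms of enrolling patients, so the two words are used almost interchangeably. Read as strictly as A1.2, criterion 3.3.2 would also bar anyone registered after the first dose, against 3.3. The loose wording is therefore already in the protocol, and A1.2 carries it into an exclusion rule.

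**Step 4: check the neighbouring row.** G1.3 covers failure to follow the registration rule. It too is manual, has no comment and is marked *All*. If someone treats the preferred 14 days as such a rule, late registrants could be excluded under G1.3 even after A1.2 is corrected.

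**Step 5: size.** The plan's only set-size calculation is in protocol 7.6. It reproduces: 1 − (1 − 0.0010)^3000 = 95.03% and 1 − (1 − 0.0016)^3000 = 99.18%, against the stated 95% and 99%. It cannot be carried further, because neither document says how many patients are registered after the first dose.

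**The case against.** The strongest reply is that context makes the meaning plain. A1.2 sits under entrance criteria, is checked by hand, and tracks 3.3.2. SAP 3 assumes that the reader knows the protocol. SAP 6.2 leaves the final decision on exclusions open until shortly before database lock, so a wrong flag can be reversed. The empty comment cell shows little, since A1.1, C1.1, G1.3 and G1.5 have none either.

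Most of this stands, and it is why the point is minor. It does not remove the defect. The intended meaning has to be inferred against the words of the row, and the protocol text that would support the inference is ambiguous in the same way. The later review helps only if those deciding depart from the written criterion.

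A reader might infer more: that the SAP will empty or badly deplete the safety set, or that the adverse drug reaction results are compromised. The documents do not support that. They foresee registration before dosing as well (the Flow Chart places it in the screening column, and 6.1 lists it under data entered before administration), they give no registration timing, and under the probable intended reading nobody is wrongly excluded. Nor do they suggest that the SAP set out to tighten the protocol's rule.

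**Conclusion.** The contradiction is real on the face of the text. As worded, A1.2 excludes from the safety and efficacy sets patients whom protocol 3.3 says to analyse. It is a minor wording defect in a rule that governs the primary-endpoint population, shared in origin with protocol 3.3.2. The number of patients affected, and any effect on the adverse drug reaction results, cannot be derived. That A1.2 was meant to catch prior use is an inference from its category, its method and the entry criteria; neither document states it.

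**What to change.** In SAP Table 6.2: 1, reword A1.2 to: *Patient had received JARDIANCE/empagliflozin before the first administration of the observed treatment course.* Keep the manual check, made against data already recorded: the pre-treatment drugs with their start and stop dates (protocol 6.2.1) and the "history of antidiabetic treatment (drug therapy, diet therapy") under protocol 5.4.1.

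Add a comment to A1.2 and G1.3 that registration after the first dose, including beyond the preferred 14 days, is not by itself a reason for exclusion.

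Add a sentence to the SAP saying that the enrolment wording in protocol 3.3.2 is read in the same way, that is, as use before the observed course. Optionally, state which exclusion in protocol 7.3 covers prior users, since that section names invalid registration without defining it.

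The cost is one reworded row, a short comment on two rows and one sentence. No new data are needed. Any flags already set under A1.2 or G1.3 should be rechecked against the new wording.

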#### Collection of AEs

The study design is of non-interventional nature and the study is conducted within the conditions of the approved marketing authorisation. Sufficient data from controlled interventional trials are available to support the evidence on the safety and efficacy of the studied BI drug. For this reason the following AE collection and reporting requirements have been defined.

The following must be collected by the investigator in the (e)CRF from first intake of JARDIANCE® Tablets at baseline visit and within 7 days (inclusive) after the last intake:

- all ADRs (serious and non-serious) as soon as possible,
- all AEs with fatal outcome in patients exposed to JARDIANCE® Tablets as soon as possible,

All ADRs, including those persisting after study completion must be followed up until they are resolved, have been sufficiently characterized, or no further information can be obtained.

The investigator carefully assesses whether an AE constitutes an ADR using the information below.

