### 7.3 PLANNED ANALYSES

The safety evaluation will be performed on the “safety set” that will include all patients who have received treatment of JARDIANCE® Tablet at least one time except those who are found to have no observation after enrolment, invalid registration, or invalid contract with the site. The efficacy evaluation will be performed on the “efficacy set”, a subset of the safety set, which will include all patients in the “safety set” except those who have no available efficacy data and/or who do not suffer from type 2 diabetes mellitus.

[figure not shown]

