6.3 PATIENT SETS ANALYSED

[figure not shown]
The following two analysis sets are defined as in NIS Protocol Section 7.3. The safety set will be the basis of all demographic, baseline and safety analyses. Efficacy analysis will be on basis of the efficacy set.

[figure not shown]
- **Safety set:**
 This patient set includes all patients who didn't have important PVs regarding safety and regulatory issues as marked "All" in [Table 6.2: 1](#).

[figure not shown]
- **Efficacy set:**
 This patient set includes all patients with JARDIANCE® in the safety set who have at least one available on-treatment HbA1c or FPG value with Type II diabetes mellitus.

[figure not shown]
Table 6.3: 1 Patient sets analysed

[figure not shown]
Class of endpoint	Patient set	
	Safety set	Efficacy set
Secondary endpoints		X
Primary endpoints, safety endpoints, demographic/baseline endpoints & treatment exposure	X	

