AE analyses will be carried out after integrating AE data from CRF and AE data from Local PV safety database (Perceive).

[figure not shown]
In addition, events coded as “no adverse event”, etc. will not be included in the AE analyses. The list of codes will be provided by Drug Safety.

[figure not shown]
Priority survey items, Important identified risk, Important potential risks and Significant ADRs

The following AEs are summarised on the basis of the Standardised MedDRA queries (SMQs) or Boehringer Ingelheim customised MedDRA query (BICMQ) by primary SOC and PT.

*:1 ADRs are also summarised.

*2: ADRs occurred in summer (the onset date is in June, July, August, or September) are also summarized.

Risk ratios with 95% confidence intervals will be shown for subgroup analyses. In case that there will be the significant difference between each factor, the frequency of patients with drug related AEs (ADRs) and with serious AEs will be summarized by primary SOC and PT. Due to the high number of exploratory subgroup analyses, it is recognised that the likelihood of chance findings is high and therefore subgroup results should be interpreted with caution.

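### SAP code G1.1 drops patients with no visit after entry, where the protocol drops only those with no observation, so a treated patient with a reported ADR or death can leave the safety set

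*SAP*

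**What the plan says.** Protocol 7.3 builds the safety set from patients who took the drug "at least one time except those who are found to have no observation after enrolment, invalid registration, or invalid contract with the site".

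SAP 6.2 turns this into codes. G1.1 is explained as "Patient made no visit after the entry". It is detected automatically and marked for exclusion from all sets. SAP 6.3 removes every patient with such a mark from the safety set, and SAP 7.8 runs all safety analyses on that set. Table 6.2: 1 makes no exception for a patient with a reported event.

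The SAP presents this as the protocol's own definition: "The following two analysis sets are defined as in NIS Protocol Section 7.3". SAP section 4 adds: "There has been no change in the planned analysis from the statistical methods described in the NIS Protocol".

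Event information does not depend on a scheduled visit. Protocol 5.3.1 has the investigator report all ADRs, and "all AEs with fatal outcome in patients exposed to" the drug, from first intake until 7 days after the last. SAP 7.8.1 then states: "AE analyses will be carried out after integrating AE data from CRF and AE data from Local PV safety database".

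**The concern.** A visit and an observation are different things. A report that a patient died, or had an ADR treated elsewhere, is naturally read as an observation after enrolment, yet it needs no visit to the study site. Such a patient belongs to the protocol's safety set and, read literally, falls outside the SAP's. The SAP brings the event in by merging the safety database and takes it out again through G1.1.

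The exclusion can also depend on outcome, because the event may be the reason for the missing visit. The first scheduled time point after baseline is week 12 (Protocol 3.1), and SAP 7.8.1 tabulates ADR onset in six two-week bands before then. Early onset is therefore of declared interest, and it is where G1.1 can act. At stake is the number of patients with ADRs, which is the primary endpoint (Protocol 5.2.1), and the tables of serious and fatal events.

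**Working it through.** **1. The rules side by side, for a treated type 2 diabetes patient with no other violation**

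| Patient after first dose | Protocol 7.3 | SAP G1.1, read literally | What is lost |
|---|---|---|---|
| No visit, no information | Out | Out | Nothing known |
| No visit, ADR reported | In, if a report is an observation | Out | One patient from the primary count |
| No visit, death judged unrelated | In, on the same reading | Out | One patient from the AE and death tables; primary count unchanged |
| Seen at the site for the event or at discontinuation | In | In, if that contact counts as a visit | Nothing |

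The two documents part company only in the second and third rows.

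**2. The plan's own figure.** Protocol 7.6 gives a 95% (99%) chance of at least one case among 3,000 completers at a true incidence of 0.10% (0.16%). The formula is 1 − (1 − p)^3000. With p = 0.0010 it gives 95.03%, and with p = 0.0016 it gives 99.18%. The figure reproduces. Neither document gives a count for G1.1.

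**3. Illustration of size.** Everything in this step is assumed: N = 3,000 treated patients; a share f with no visit; ADR incidence p = 10% among those with a visit; and a share q of no-visit patients with a reported ADR.

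- ADR patients lost = N·f·q
- Incidence under G1.1 = p
- Incidence keeping only no-visit patients with a report = [N(1−f)p + Nfq] / [N(1−f) + Nfq]
- Incidence with all treated patients in the denominator = (1−f)p + fq

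Example, f = 1% and q = 10%: 30 patients have no visit, and the other 2,970 include 297 with an ADR. Lost: 30 × 0.10 = 3. Keeping those three gives 300/2,973 = 10.09%. Using all treated gives 300/3,000 = 10.00%.

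| f | q | ADR patients lost | Under G1.1 | Keep reported only | All treated |
|---|---|---|---|---|---|
| 0.5% | 10% | 1.5 | 10.00% | 10.05% | 10.00% |
| 1% | 1% | 0.3 | 10.00% | 10.01% | 9.91% |
| 1% | 10% | 3 | 10.00% | 10.09% | 10.00% |
| 1% | 30% | 9 | 10.00% | 10.27% | 10.20% |
| 5% | 30% | 45 | 10.00% | 11.40% | 11.00% |

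In the most extreme row shown, changing p to 5% gives 6.48% (keep reported only) and 6.25% (all treated). Changing p to 15% gives 16.32% and 15.75%.

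Two things follow. The count of ADR patients can only fall under G1.1. The incidence against all treated patients can move either way: G1.1 understates it when q exceeds p and overstates it when q is below p.

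**4. A rare ADR.** Let a share h of its cases fall in excluded patients, with n = 3,000 borrowed as a round number. The chance of seeing at least one case is 1 − [1 − 0.0010(1 − h)]^3000: 95.0% at h = 0, 93.3% at h = 10%, 89.5% at h = 25% and 77.7% at h = 50%. The values of h are assumptions.

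**The case against.** The strongest reply is that G1.1 is a loose paraphrase of the protocol's rule. Neither visit nor entry is defined for this code. An adverse event itself triggers eCRF entry (Protocol flow chart and 3.1), and assessments are filed under the nearest visit (Protocol 6.1), so a patient with an eCRF-reported ADR may already have a post-baseline record. Protocol 3.3 calls a patient entered only once post-drug data have been transmitted. Automated may describe how the violation is found, and SAP 6.2 leaves the final exclusions to decisions taken before database lock. The table also files G1.1 under invalid registration, which the protocol excludes too.

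Much of this shows that the literal result is not inevitable. None of it supplies a rule that keeps the patient. Protocol 7.3 lists absence of observation separately from invalid registration, and failing to return does not make a registration invalid. Case-by-case decisions in a single-group study would be made with the events in view.

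Other objections stand and limit the point:

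- A reader might infer that the earliest and most severe events drop out in general. The documents do not support that. Only patients with no post-entry visit at all are affected, and a visit for the event or at discontinuation (Protocol 6.2.3) may count.
- A non-fatal hospitalisation judged unrelated need not be collected under Protocol 5.3.1, so G1.1 is not what loses it.
- A reader might infer that the sample size statement is undermined. It concerns completers, who have made visits; step 4 only borrows its n.
- The reports still reach the sponsor and the authorities (Protocol 5.3.1 and 5.3.2). What is at risk is the count in the study tables, in a descriptive study.
- Keeping no-visit patients because they had an event makes membership depend on outcome in the other direction.

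**Conclusion.** The mismatch is real and undeclared. As worded, G1.1 can remove a treated patient whose ADR or fatal event the sponsor holds and intends to merge, and nothing in the SAP says otherwise. This rests on reading a reported event as an observation and on the patient having made no visit of any kind.

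The size cannot be computed from the documents. Over the assumed values in the table, the loss runs from 0.3 to 45 ADR patients, and retaining those with a report moves a 10% incidence by between 0.01 and 1.4 percentage points. The upper end needs 5% of patients without a visit and 30% of them with a reported ADR. A small effect on the overall rate is the more likely outcome. For a rare, early, serious or fatal ADR, a few lost patients could matter. A certain downward bias in the ADR incidence should not be claimed, because the denominator changes as well.

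**What to change.** Reword G1.1 to match Protocol 7.3, for example: *no post-first-dose observation from any source (eCRF or safety database)*. A treated patient with a reported AE, ADR or death and no other exclusion then stays in the safety set. Check G1.1 patients against the safety database before the sets are fixed, and list all of them with any known events.

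Because retention would then depend partly on having an event, also report ADR incidence with all treated no-visit patients in the denominator, or with and without the retained patients. The first alternative treats patients without a report as event-free and so tends to err low. Keeping only those with a report tends to err high.

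The cost is one line of SAP text, a cross-check against a database already being merged, one listing and one extra incidence figure. The downside is the small upward pull from the retained patients, which the second figure makes visible.
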